Study Title: Nudges and Incentives to Enhance the Opioid Treatment Workforce

Funder	NIDA
Study Rationale	
Opioid overdoses currently claim the lives of 115 Americans per day. This epidemic is alarming, not just in its effects on the lives of individuals and families, but also on the light it has shined on the disturbing lack of treatment options in many areas. A number of effective treatments are available for opioid use disorder, but many require special training beyond a professional degree. In addition, the complex comorbidities and life circumstances faced by those with an opioid use disorder can deter many providers from investing the time needed to learn how to diagnose and treat individuals needing these services. To date, of North Carolina's 8087 primary care physicians, 4669 nurse practitioners, and 4237 physician assistants, only 785 (<5%) have undergone the waiver training required to provide medication assisted treatment (MAT) for opioid use disorder, a minuscule number of North Carolina's primary care workforce. Many waiver-trained providers are not yet prescribing, due in part to the lack of on-going education or support, so the effective rate of treatment provision is substantially lower than 5%. Further, only one-fifth of NC's zip codes have a waiver-trained provider. ECHO is an evidence-supported hub-and-spoke model of professional development that uses video conferencing technology to bring experts into even the most rural areas to support primary care providers. ECHO for MAT is program in NC that uses the ECHO model to develop a provider workforce that is equipped to provide MAT to those in need of treatment, preventing further accidental deaths from overdose. The time commitment required to develop MAT proficiency can prove to be a barrier to take up since provider time participating in ECHO may represent lost revenue from not seeing patients. This challenge can especially prohibit participation from small and rural practices, often where treatment is most needed. This research project will conduct a pilot study to examine the extent to which informational nudges incorporating specific information from a provider's community into recruitment materials (Aim 1) and financial incentives (Aim 2) affect participation in ECHO MAT by primary care providers. Through these estimates, this study will contribute much-needed information on the incentives that can be used to create a behavioral health workforce that is ready to meet the challenges of the opioid epidemic.


Nudges and Incentives to Enhance the Opioid Treatment Workforce

Study Objective(s)	Aim 1: To estimate the influence of informational nudges on the engagement of primary care providers in an opioid treatment learning collaborative to address the opioid overdose crisis. Aim 2: To estimate the influence of financial incentives on the participation intensity of primary care providers in an opioid treatment learning collaborative to address the opioid overdose crisis.
Study Design	The study is designed to be implemented in two phases. Phase 1 is the recruitment phase. Providers will be randomized to receive recruitment letters and emails from 1 of 4 conditions. Randomization for this phase will occur at the practice level, as determined by provider address. Participants that contact the study team and enroll in the study will begin Phase 2 of the study. In Phase 2 of the study participants will be randomly assigned to rewards for participation in ECHO MAT learning collaborative. Their participation in the learning collaborative will be tracked. Phase 2 of the study is a pilot.
Subject Population	Inclusion Criteria
key criteria for Inclusion and Exclusion:	
1. Licensed practicing Primary Care Provider (MD, DO, PA, NP)2. Currently practicing in NC, not currently participating in ECHO MAT Exclusion Criteria 
1. Another member of the same practice is already enrolled in the study (one provider per practice in Phase 2)2. Active participation in The University of North Carolina at Chapel Hill (UNC) ECHO Collaborative at beginning of study
Number of Subjects	Up to 80 to achieve at least 20 in each reimbursement arm
Study Duration	Each subject's participation will last six months with the exception of participants who had not completed as of 3/9/2020 whose participation was extended by 3 months due to decreased learning collaborative sessions resulting from COVID-19. The entire study is expected to last up to two years
Study Phases	(1) Recruitment : recruitment materials (letters or emails) sent once randomized to 1 of 4 conditions. Once participant enrolls, then
Screening	
Study Treatment	
Follow-Up	(2) Randomization to 1 of 3 study arms: enrolled participants are re-randomized to 1 of 3 levels of reimbursement to estimate the influence of financial incentives in participation in learning collaboratives to address the opioid overdose crisis. Participation in learning collaboratives over 6 months will be

Nudges and Incentives to Enhance the Opioid Treatment Workforce

tracked. Participation in learning collaboratives will be tracked over 9 months for participants who did not complete as of 3/9/2020 due to the COVID-19 pandemic.

Safety Evaluations	The risk to participants is minimal.
Statistical and Analytic Plan	
In Aim 1, we anticipate starting with a random selection of 600 providers from the list of eligible NC providers generated from the NPI Registry, limiting to primary care providers identified through taxonomy codes, which gives more than 90% power to detect a ten percentage point difference in the binary outcome, response to study recruitment. We will use binary models (logit, linear probability models) to examine response to recruitment as a function of study arm, controlling for provider type and county fixed effects.
 
For Aim 2, we will randomly recruit up to 80 providers as needed to have at least 20 providers per arm enrollees for this phase of the pilot (20 providers per arm). The outcome to be monitored for Aim 2 is the number of ECHO sessions attended in the 6 months following randomization. Because this is a pilot study, the sample size is not powered for the primary outcome, number of ECHO clinics attended. We will conduct a negative binomial or other count data model (depending on statistical tests) of the number of sessions as a function of financial incentive arm to estimate the effect of financial incentives on participation.

DATA AND SAFETY MONITORING PLAN	The risk to participants is minimal, and this does not meet the definition of a clinical trial, thus there is no data safety monitoring plan.

1 BACKGROUND AND RATIONALE

The major goals of the project are:

Aim 1: To estimate the influence of informational nudges on the engagement of primary care providers in an opioid treatment learning collaborative to address the opioid overdose crisis. Primary care providers in North Carolina, including physicians, nurse practitioners, and physician assistants, will be randomly assigned to receive either a pro-social recruitment approach for participating in the UNC ECHO MAT intervention or standard recruitment practice. Treatment assignment will provide pro-social information, including customized figures on the opioid use epidemic in the provider's region and the degree of the provider shortage in their region. The comparison arm will include a standard approach to recruitment that does not contain a pro-social recruitment message. Analysis of this data will provide estimates of the degree of responsiveness of providers to informational nudges.

Aim 2: To estimate the influence of financial incentives on the participation intensity of primary care providers in an opioid treatment learning collaborative to address the opioid overdose crisis. At the second stage, providers agreeing to enroll in the program will be re-randomized to one of three levels of reimbursement for time spent participating in the UNC ECHO MAT intervention. Analysis of this data will provide causal estimates of the degree of responsiveness of provider participation intensity to financial incentives. A sub-aim will examine whether the effect of incentives on participation intensity varies between the pro-social recruitment group and status-quo recruitment group. The results from this study will inform the feasibility and design of a full-scale trial testing the effects and cost-effectiveness of approaches to address the shortage of adequately trained primary care clinicians, providing urgently needed information on best practices in developing the health care workforce to treat individuals and communities most affected by the opioid crisis.

1.1 Introduction

This project seeks to examine a critical barrier to optimizing the health care workforce for the treatment of opioid use disorders. Without a dramatic increase in the number of primary care providers trained and comfortable with the many nuances of prescribing medication-assisted treatment (MAT), the staggering increases in opioid overdose deaths will continue to skyrocket. However, Drug Addiction Treatment Act (DATA) 2000 waiver training alone is not enough to facilitate prescribing for patients who desperately need services; an estimated 40% of physicians with waivers do not initiate MAT prescriptions. To address this problem, North Carolina developed a learning collaborative framework to promote MAT training. Learning collaboratives have been shown to be an efficacious approach to increase utilization of MAT, but engagement among providers in North Carolina has been low. To date, the need to encourage provider collaborative participation at scale has not been addressed. This is the critical problem focused on in this study.

The death rate from accidental opioid overdoses continues to climb at an alarming rate, with overdose deaths in 2016 almost five times the number from 1999. The daily death rate from opioid overdoses in the U.S. alone is now estimated at 115, so every day that evidence-based treatment is not available leads to more preventable deaths. North Carolina is one of the states with both an opioid overdose death rate greater than the national average (11.9 vs 10.4 deaths per 100,000, age-adjusted)

Nudges and Incentives to Enhance the Opioid Treatment Workforce

and a rate of increase in opioid overdose deaths greater than the national average (19% vs. 16%). North Carolina is also one of four states with an Agency for Healthcare Research and Quality (AHRQ) funded Extension for Community Healthcare Outcomes (ECHO) MAT learning collaborative available to primary care practices, but engagement among providers is low. While the main barriers to engagement are incompletely understood, recent evidence from provider interviews conducted by the study team in December 2017 and January 2018 suggest that one substantial barrier is the time required for weekly ECHO clinics.

1.2 Name and Description of Investigational Product or Intervention

Receipt of recruitment letter is the Intervention for Aim 1.

Randomized to one of three levels of financial reimbursement for their time in the ECHO sessions is the intervention for the second level of the study.

1.3 Non-Clinical and Clinical Study Findings

Potential Benefits. This study seeks to determine the extent to which financial incentives and informational nudges increase the participation of providers in a learning collaborative to support the expansion of MAT, thereby increasing the percentage of physicians, who get DATA-2000 waiver training and certified to provide MAT, who go onto implementation this lifesaving evidence-based practice in underserved counties.

Potential Risks. The potential risks of the intervention are minimal and patients in the care of these medical practices may benefit by having more decision-making involvement in their care and access to needed MAT. There is a small risk of breach of confidentiality. Procedures will be taken to minimize the possibility of a breach in confidentiality. No subjects will be identified in any publication or report of this study. There is no medical risk or risk of physical discomfort from this study.

2 STUDY OBJECTIVES

This research project will conduct a pilot study to examine the extent to which informational nudges incorporating specific information from a provider's community into recruitment materials (Aim 1) and financial incentives (Aim 2) affect participation in ECHO MAT by primary care providers. Through these estimates, this study will contribute much-needed information on the incentives that can be used to create a behavioral health workforce that is ready to meet the challenges of the opioid epidemic.

2.1 Primary Objective

Aim 1: To estimate the influence of informational nudges on the engagement of primary care providers in an opioid treatment learning collaborative to address the opioid overdose crisis. Primary care providers in North Carolina, including physicians, nurse practitioners, and physician assistants, will be randomly assigned to receive either a pro-social recruitment approach for participating in the UNC ECHO MAT intervention or standard recruitment practice. Treatment assignment will provide pro-social information, including customized figures on the opioid use epidemic in the provider's region and the

Nudges and Incentives to Enhance the Opioid Treatment Workforce

degree of the provider shortage in their region. The comparison arm will include a standard approach to recruitment that does not contain a pro-social recruitment message. Analysis of this data will provide estimates of the degree of responsiveness of providers to informational nudges.

Aim 2: To estimate the influence of financial incentives on the participation intensity of primary care providers in an opioid treatment learning collaborative to address the opioid overdose crisis. At the second stage, providers agreeing to enroll in the program will be re-randomized to one of three levels of reimbursement for time spent participating in the UNC ECHO MAT intervention. Analysis of this data will provide causal estimates of the degree of responsiveness of provider participation intensity to financial incentives.

2.2 Secondary Objective

A sub-aim will examine whether the effect of incentives on participation intensity varies between the pro-social recruitment group and status-quo recruitment group.

3 INVESTIGATIONAL PLAN (brief overview)

3.1 Study Design

In the first level of the study, providers will be randomized to receive one of two different recruitment letters. **The receipt of the letter is the intervention for Aim 1.** We will follow providers for up to 6 months after the mailing of the recruitment letters to monitor whether they attempted to sign up for the ECHO learning collaborative. This is the primary outcome for Aim 1.

Among the providers who contacted the study coordinator with interest in participating in the ECHO MAT learning collaborative (up to 80 of the providers), we will obtain consent to participate in the second level of the study, where providers will be **randomized to one of three levels of financial reimbursement for their time in the ECHO sessions. This is the intervention for the second level of the study.** We will monitor the number of sessions attended over 6 months from enrollment (9 months from enrollment for participants who did not complete as of 3/9/2020). This is the outcome for the second level of the study. We will send a letter to inform participants on how much they have participated and, if applicable, their incentive amount.

We may ask up to 44 of the study participants to participate in key informant interviews once their participation in the study has ended (6 months after enrollment). We will also contact a few individuals who initially indicated they were interested in participating, but then did not complete the consent process. We hope to learn why they did not complete the enrollment process.

We will contact study participants to notify them that we will look up their Waiver 2000 status (this is available through the DEA and publicly available on SAMHSA's website). We will not post or publish individual provider specific information on Waiver status.

Nudges and Incentives to Enhance the Opioid Treatment Workforce

We will use Medicaid claims data and ECHO learning collaborative participation data for the participants in our study to examine if the interventions in phase 1 or 2 have changed their MAT prescribing behavior, or their participation in ECHO MAT learning collaboratives.

Recruitment: Primary care providers will receive recruitment letters and may receive emails and phone calls based on the recruitment condition they are assigned to.

Randomization:

Phase 1: Primary care providers will be randomized by practice to 1 of 4 study arms. Computerized randomization will assign practices to study arms, practices and primary care providers will have an equal chance of being randomized to each study arm.

Phase 2: Eligible participants will be randomized to the Phase 2 study arm upon enrollment in the study. Randomization will be assigned using a predetermined randomly ordered list of study condition assignments. Upon enrolling in the study, the participants will be assigned to the condition that is next on the list. Participants will have an equal chance of being randomized to each study arm.

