3.2 Allocation to Treatment Groups and Blinding (if applicable)

Participants are randomized to receive 1 of 4 recruitment materials. Once enrolled, participants are then randomized to receive 1 of 3 financial reimbursements for attendance in ECHO sessions

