10 DATA COLLECTION AND MANAGEMENT

Procedures will be taken to minimize the possibility of a breach in confidentiality. No subjects will be identified in any publication or report of this study.

The nature of practice level data is ordinary, and unlikely to include socially stigmatizing conditions for providers. Secondary claims data will also be stored in secure databases. All working files are limited data sets, with patient names and contact information stripped off, but containing identified information on providers using a unique identifier (NPI) allowing linkage to data sources such as Medicaid prescribing information. This file will remain with the PI; the other research staff will access only files without patient names, addresses and other direct identifiers.

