11 RECRUITMENT STRATEGY

PCPs will be identified from provider lists obtained through the NC Medical Board for physicians and physician assistants and the NC Board of Nursing for nurse practitioners. We will also use the DATA-2000 database of providers to help us identify PCPs who do not have waivers. Providers who are prescribing to Medicaid beneficiaries will be determined from NC Medicaid claims data, which is in use for the ECHO MAT study, and has been IRB approved for re-use for the ECHO Nudges study. We will use the list of providers currently participating in ECHO MAT, available to study investigators, to exclude the providers currently participating in ECHO (n=24). Once the denominator of eligible providers has been determined, the ECHO Nudges study team will randomly select providers in groups of 600 to randomize for pro-social or recruitment as usual invitations to participate in ECHO Nudges (and therefore ECHO MAT). From the group who decide to participate (outcome for Aim 1), we will re-randomize to one of the three arms of financial incentives. Effort to recruit providers for the Aim 2 analysis will follow immediately from the Aim 1 retention effort (e.g., providers must agree to participate in ECHO to be randomized to Aim 2). The number of sessions of participation within six months of engagement will be the Aim 2 outcome, thus no further efforts on retention will be utilized for the ECHO Nudges study.

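### The exploratory comparison of Phase 1 letters on MAT prescribing and ECHO participation, read naturally, is restricted to enrolled providers and so is not protected by randomization

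*Combined protocol and SAP*

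**What the plan says.** Section 3.1 (Study Design) states that Medicaid claims and ECHO attendance data will be used "for the participants in our study to examine if the interventions in phase 1 or 2 have changed their MAT prescribing behavior". The same sentence names ECHO attendance as a second outcome. This asks a causal question about the Phase 1 letters as well as the Phase 2 incentives, in one stated set of people.

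The documents use *participants* in two ways:

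- **Enrolled providers.** The Study Design row of the synopsis says "Participants that contact the study team and enroll in the study will begin Phase 2 of the study". Section 3.1 itself says "We may ask up to 44 of the study participants to participate in key informant interviews once their participation in the study has ended", and dates that end six months after enrollment. Section 3.3 limits the number of subjects to 80. Appendix Table 1 starts the session and prescribing windows at enrollment.
- **Everyone sent a letter.** Section 3.2 says "Participants are randomized to receive 1 of 4 recruitment materials", which places participants before enrollment.

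Appendix Table 1 makes completed enrollment a secondary outcome of Phase 1, and Section 11 calls the decision to participate the Aim 1 outcome. Table 1 lists sessions and MAT prescribing for Phase 2 comparisons only. Section 6.1 gives no model for a letter effect on either.

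**The concern.** Randomization makes the letter groups comparable among all providers who were mailed. It does not make the enrollees of one letter comparable with the enrollees of another, because the letter helps decide who enrolls. If a prosocial letter brings in providers who are less committed on average, its enrollees will prescribe and attend less even if the letter changed nobody's prescribing. The better a letter recruits, the more room there is for this distortion.

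At stake is the reading of a secondary result. A difference among enrollees could be reported as an effect of the letter on prescribing or attendance when it only reflects who was recruited.

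**Working it through.** **The plan's own figure.** No figure is given for a letter effect on prescribing or sessions. The nearest is Section 6.1: more than 90% power for a ten-point difference in response with 600 providers. Assume two-sided 5%, independence, 300 v 300 on the prosocial factor, and 5% v 15%. The null standard error is √(2×0.10×0.90/300) = 0.0245 and the alternative one is √((0.0475+0.1275)/300) = 0.0242. Then z = (0.10 − 1.96×0.0245)/0.0242 ≈ 2.15, so power is 98.4%. The claim is attainable at low control rates (93.1% at 10%, but 80.9% at 20%). It cannot be confirmed, because the control rate and alpha are not stated. The present point does not depend on it.

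**Inputs for the illustration (assumptions, not in the documents).** Enrollment is 5% under the usual letter and 15% under the prosocial letter. From 300 v 300 this gives 15 + 45 = 60 enrollees, the minimum in Section 6.1. Prescribing prevalence is 5% in both groups, so the letter has no effect on it. A provider enrolls when a standard normal motivation score u exceeds t = Φ⁻¹(1 − e), where e is the enrollment rate: t = 1.645 for 5% and 1.036 for 15%. A normal prescribing liability with cut-off c = 1.645 has correlation ρ with u.

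**Step 1: prescribing.** Among enrollees, P(prescribes) = Φ₂(−t, −c; ρ)/e, where Φ₂ is the bivariate normal distribution function.

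| ρ | Usual, enrollees | Prosocial, enrollees | All mailed, both letters |
|---|---|---|---|
| 0.5 | 0.01219/0.05 = 24.4% | 0.02484/0.15 = 16.6% | 5% |
| 0.3 | 0.00713/0.05 = 14.3% | 0.01659/0.15 = 11.1% | 5% |
| 0.1 | 0.00371/0.05 = 7.4% | 0.01011/0.15 = 6.7% | 5% |
| 0 | 0.00250/0.05 = 5% | 0.00750/0.15 = 5% | 5% |

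The true letter effect is zero in every row. The spurious gap runs from 7.8 points to none.

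**Step 2: sessions.** Assume expected sessions of exp(1.2 + 0.5u) for a provider who enrolls and zero otherwise. The mean per enrollee is exp(1.325) × Φ(0.5 − t)/e.

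- Usual: 3.762 × 0.1261/0.05 = 9.5 per enrollee; × 0.05 = 0.47 per mailed provider.
- Prosocial: 3.762 × 0.2958/0.15 = 7.4 per enrollee; × 0.15 = 1.11 per mailed provider.

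The usual letter looks better among enrollees, while the prosocial letter yields more sessions per mailed provider. The direction reverses.

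**Step 3: does the direction depend on the assumptions?** Use three groups instead of a correlation. Suppose 5% enroll under either letter and 40% of them prescribe. A further 10% enroll only under the prosocial letter and prescribe at rate q whichever letter they get, so the letter again has no effect. Usual enrollees prescribe at 40%; prosocial enrollees at (0.05×0.40 + 0.10×q)/0.15.

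- q = 10%: 20.0%, a difference of −20.0 points.
- q = 40%: 40.0%, no difference.
- q = 60%: 53.3%, a difference of +13.3 points.

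The enrolled-only contrast is unbiased here only when the providers brought in by the letter match the others on the outcome, or when the letter brings in nobody extra.

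**The case against.** **The reading is an inference.** Section 3.2 applies *participants* to everyone sent recruitment materials. Section 10 describes files "containing identified information on providers using a unique identifier (NPI) allowing linkage to data sources such as Medicaid prescribing information", and Section 11 says "Providers who are prescribing to Medicaid beneficiaries will be determined from NC Medicaid claims data", so an analysis of all mailed providers is not ruled out. This stands in part: the documents do not settle the analysis set. The nearby uses in Section 3.1 and the Table 1 windows still favor enrollees. If all mailed providers were meant, the plan has no prescribing window for those who never enroll.

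**It is one exploratory sentence.** It sits in a section headed as a brief overview, and neither Table 1 nor Section 6.1 carries a letter effect on prescribing or sessions. This stands, and it limits the weight of the point.

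**The size is assumed.** No document gives enrollment by letter, prescribing prevalence or any correlation. This stands, so the result is shown as a range. With 15 v 45 enrollees, the 7.8-point gap has a standard error of √(0.244×0.756/15 + 0.166×0.834/45) = 12.4 points and a 95% interval of about −17 to +32. A statistically significant false finding is therefore unlikely, though a point estimate could mislead.

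**A stronger reading.** A reader might infer that the trial will report a harmful prosocial letter, or that prescribing results will be reversed. The documents do not support that. Step 1 shows a spurious gap rather than a reversal, only the sessions illustration changes sign, and Step 3 shows that the bias can run either way.

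**Conclusion.** The concern holds as a point about one exploratory analysis. Followed in its natural reading, Section 3.1 compares letters among providers selected by an outcome of those letters, and the plan provides no adjustment for that selection. Under the stated assumptions, the false prescribing gap ranges from zero to about 8 points across correlations of 0 to 0.5, and the sessions comparison can change direction. These figures show what is possible; they do not predict this trial's results.

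The Phase 1 contact and enrollment outcomes are counted among all recruited providers and are unaffected. The Phase 2 incentive contrasts are randomized after enrollment and are also unaffected. For the sub-aim in Section 2.2, incentive effects within each letter group remain randomized, but a difference between letter groups also reflects whom each letter brought in.

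**What to change.** State in Sections 3.1 and 6.1 that any Phase 1 contrast on prescribing or ECHO participation:

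- includes every randomized provider, by assigned letter;
- uses a window that starts at mailing and has the same length for all;
- counts zero sessions for providers who never attend;
- links Medicaid prescribing by NPI;
- uses standard errors clustered by practice, the unit of Phase 1 randomization.

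Keep the enrolled-only set for Phase 2 contrasts.

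Section 12 takes consent only at the start of Phase 2, and Section 11 mentions approval for claims re-use in the context of identifying providers. Confirm that this approval covers outcome analysis of providers who neither enrolled nor consented. If it does not, label the enrolled-only letter comparison of prescribing descriptive and draw no causal conclusion; that costs only wording. The zero-count rule still allows attendance to be compared in everyone randomized.

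The full fix costs some extra linkage and analysis, and estimates per mailed provider will be numerically small.

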6 STATISTICAL CONSIDERATIONS

6.1 Statistical Methods

In Aim 1, we anticipate starting with a random selection of 600 providers from the list of eligible NC providers received from the NC Board of Medicine and NC Nursing Board, limiting to primary care providers identified as primary care through their provider type, which gives more than 90% power to detect a ten percentage point difference in the binary outcome, response to study recruitment. We will use binary models (logit, linear probability models) to examine response to recruitment as a function of study arm, controlling for provider type and county fixed effects.

For Aim 2, we will randomly recruit at least 60 enrollees (and up to 80 to enroll at least 20 providers per arm of this phase). The outcome to be monitored for Aim 2 is the number of ECHO sessions attended in the 6 months following randomization. Because this is a pilot study, the sample size is not powered for the primary outcome, number of ECHO clinics attended. We will conduct a negative binomial or other count data model (depending on statistical tests) of the number of sessions as a function of financial incentive arm to estimate the effect of financial incentives on participation.

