8 STUDY INTERVENTION ADMINISTRATION

Phase 1 recruitment letters are designed in a 2 (prosocial mention of need for primary care providers trained in opioid use disorder treatment vs. none) x 2 (mention of additional financial supports available for participation in training vs. none). This yields 4 study conditions for recruitment letters:

- 1) Letter including prosocial messages and additional mention of practice supports available for participation,
- 2) Letter including prosocial messages but no additional mention of financial support available for participation,
- 3) Letter including an additional mention of financial support available for participation but no prosocial messages, and
- 4) Recruitment as usual letter that does not include prosocial messages or an additional mention of financial support available for participation.

Phase 2 examines participation in the learning community by group. Participants will be randomly assigned to 1 of 3 groups. The investigators are not disclosing the Phase 2 conditions until the end of the study, as approved by UNC's institutional review board (IRB).

At the end of data collection, we will send a debriefing form to all participants to share the information that we withheld from them at the beginning of the study.

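### Phase 1 assigns practices with no county strata described, while the Aim 1 models condition on county: this costs precision, by an amount the documents do not let one fix

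*Combined protocol and SAP*

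**What the plan says.** The unit of assignment is the practice. The synopsis (Study Design) states: "Randomization for this phase will occur at the practice level, as determined by provider address". County can therefore be known before the letters are drawn.

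Section 3.1 (Randomization, Phase 1) gives the method: "Primary care providers will be randomized by practice to 1 of 4 study arms"; "Computerized randomization will assign practices to study arms"; and "practices and primary care providers will have an equal chance of being randomized to each study arm". It names no stratification factor, blocking or other balancing device.

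Section 8 describes a 2 x 2 layout of pro-social message and mention of financial support: "This yields 4 study conditions for recruitment letters".

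For the analysis, section 6.1 says "we anticipate starting with a random selection of 600 providers" and specifies logit and linear probability models of response by arm, "controlling for provider type and county fixed effects". The synopsis repeats this model. Section 11 allows for more than one wave: the team will "randomly select providers in groups of 600 to randomize for pro-social or recruitment as usual invitations".

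The number of counties, practices per county, sampled providers per practice, baseline response rate and significance level are not given.

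**The concern.** A county fixed effect removes every between-county contrast. What remains is the comparison of letters among practices in the same county, and the assignment as described does nothing to balance those comparisons. A county with one sampled practice adds nothing to the letter effect, nor does a county whose practices all drew the same level. Counties that stay in but are split unevenly contribute less than they could.

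At stake is the precision of the primary Aim 1 comparison. Its only stated support is a power above 90%, given without any allowance for the county effects. The loss is greatest where few practices are sampled per county. Those may well be the small and rural settings that the rationale stresses, though the documents do not show this.

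**Working it through.** **1. The plan's power figure.** Baseline and alpha are not stated; I assume two-sided 0.05. For 600 providers, one letter factor compares about 300 v 300. Pooled-variance formula: power = Φ[(δ√n − 1.96√(2p̄(1−p̄))) / √(p1(1−p1)+p2(1−p2))].

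For 10% v 20%: (0.1 × 17.32 − 1.96 × 0.505) / 0.5 = 1.48, giving 93.1%. Other baselines give 98.4% (5 v 15%), 90.5% (12 v 22%) and 86.7% (15 v 25%). The stated figure is therefore met for a baseline up to about 12%, with no allowance for county effects.

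**2. Information in one county.** With m sampled practices, q of them on one level of the factor, the county contributes q(m−q)/m. An even split gives m/4. Under a simple 1:1 draw, E[q(m−q)] = m(m−1)/4, so the expected share kept is (m−1)/m:

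| m | simple draw keeps |
|---|---|
| 1 | 0% |
| 2 | 50% |
| 3 | 67% |
| 6 | 83% |

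**3. All counties together.** Summing over C counties with at least one sampled practice, and M practices in all, the share kept is 1 − C/M. For 600 single-provider practices in 50 equal counties this is 1 − 50/600 = 91.7%; simulation gave 91.9%. With 100 equal counties, about 99.7 non-empty, it is 1 − 99.7/600 = 83.4%; simulation gave 83.5%.

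**4. Why merging matters.** A block of the four letters puts two practices on each level of each factor, so a stratum of four keeps 100%. If a county has only two practices in such a block, both get the same level one time in three, and 67% is kept. A single-practice county is lost under county-only blocking too.

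**5. Loss against blocks in pooled strata.** Assumed inputs: log-normal county sizes with coefficient of variation 0.8-1.6, and strata merged to at least four practices. With 100 counties and 300-500 practices, the simple draw with county effects keeps about 72-84% and the pooled blocked design about 99%. At the low end the loss is 1 − 0.72/0.99 = 27%; at the high end, 1 − 0.84/0.99 = 15% from these rounded shares, 16% unrounded.

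| assumed counties | practices | loss |
|---|---|---|
| 100 | 300-500 | 16-27% |
| 50 | 300-500 | 9-15% |
| 20 | 300-500 | 4-6% |
| 20-100 | 1,000 | 2-9% |

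**6. Source of the loss.** Here the benchmark is balance within each unmerged county, with 100 counties. Counties holding a single letter level account for 4.5 of 15.0 points (equal sizes, one provider per practice) and 5.0 of 11.7 (log-normal sizes, SD 1.0, one provider per practice). With equal sizes and three providers per practice they account for 25.6 of 30.2. The rest is chance imbalance in counties that stay in.

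**7. Effect on power** (300 v 300, n scaled by the information kept):

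| loss | 5 v 15% | 10 v 20% |
|---|---|---|
| 0 | 98.4% | 93.1% |
| 5% | 98.0% | 91.9% |
| 11% | 97.3% | 90.1% |
| 16.7% | 96.3% | 88.1% |
| 25% | 94.5% | 84.6% |
| 27% | 93.9% | 83.7% |

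This treats providers as independent and is only a guide.

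**The case against.** **Silence is not denial.** Section 3.1 is a short description inside a brief overview. It does not say that the draw was simple, so strata may have been used. This stands, and the first request is to state it.

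**The size rests on assumptions.** Every input to the loss is assumed, and further groups of 600 would shrink it. This stands: 16-27% is not a property of the plan, and with few counties or many practices the loss is minor.

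**County effects also bring a benefit.** They absorb between-county variation in response, and the information index gives no credit for that. This stands as a reason to keep geographic adjustment. It is no reason to leave the draw unbalanced on it.

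**It is late.** The extension for participants not finished by 3/9/2020 shows that letters had gone out and enrolment had begun. A change in assignment can reach only later groups, if there are any.

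A reader might also infer more than the documents support:
- *That the whole loss comes from counties dropping out.* Step 6 shows that this part can be less than half.
- *That the letter effect is biased.* Assignment is random either way, so only precision suffers.
- *That the stated power is refuted.* At a 5% baseline it survives even a 27% loss; at 10% it does not survive a loss of 16.7% or more. The plan gives no baseline.
- *That stratifying cures every loss from sparse counties.* In a logit with county dummies, counties without a responder also drop out, which is a separate matter.

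**Conclusion.** The concern holds as one of precision. The described assignment does not balance the grouping on which the Aim 1 models condition, and the expected cost of a simple draw is C/M of the information. How large that is depends on counts that the plan does not give. It is worth correcting if the sample spreads over many counties with few practices each, and small if it covers about 20 counties or grows to 1,000 practices. These ranges rest on the assumed county numbers and size spread, on one two-level letter factor, and on section 3.1 being a complete description of the draw.

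**What to change.** 1. In 3.1, state whether Phase 1 was stratified by county or region, and give the numbers of practices and counties sampled so that C/M can be computed.
2. For any group of 600 not yet mailed, assign the four letters in permuted blocks within county. Merge small neighbouring counties until each stratum has at least four practices. In 6.1, use those strata as the fixed effects in place of single counties.
3. For groups already mailed without strata, replace the single-county dummies in 6.1 by the same merged strata, defined without reference to response. This gives about 6-14% more information at 100 counties and 300-500 practices, depending on the merging rule, and little if counties are few. It cannot undo the chance imbalance already drawn.

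The cost is a change to the assignment program for later groups and a few lines in 3.1 and 6.1, with no added providers or letters. The small downside is coarser geographic adjustment where counties are merged.
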